13.4. Duration of Response

13.4.1 Duration of overall response

The duration of response (DOR) is measured from the time measurement criteria are met for CR or PR (whichever is first recorded) until the first date that recurrent or progressive disease is objectively documented (taking as reference for progressive disease the smallest measurements recorded since the treatment started). The duration of overall CR is measured from the time measurement criteria are first met for CR until the first date that recurrent disease is objectively documented.

13.4.1 Duration of stable disease

Stable disease is measured from the start of the treatment until the criteria for progression are met, taking as reference the smallest measurements recorded since the treatment started.

13.5. Immune-Related Response Criteria

13.5.1 Increasing clinical experience indicates that traditional response criteria (e.g. Response Evaluation Criteria in Solid Tumors, Version 1.1 [RECIST v1.1] and World Health Organization [WHO]) may not be sufficient to fully characterize activity in the new era of targeted therapies and/or biologics. In studies with cytokines, cancer vaccines, and monoclonal antibodies, complete response, partial response, or stable disease have been shown to occur after an initial increase in tumor burden characterized as progressive disease according to traditional response criteria. Therefore, conventional response criteria may not adequately assess the activity of immunotherapeutic agents because progressive disease (by initial radiographic evaluation) does not necessarily reflect therapeutic failure. Long-term effect on the target disease must also be captured. Immune-related response criteria (irRC) attempt to enhance characterization of new response patterns that have been observed with immunotherapeutic agents (e.g. ipilimumab and nivolumab).

13.5.2 Glossary of Immune-Related Response Terminology

Term	Definition
SPD	Sum of the Products of the two largest perpendicular Diameters
Tumor burden	$SPD_{\text{index lesions}} + SPD_{\text{new, measurable lesions}}$
Nadir	minimally recorded tumor burden
irCR	immune-related Complete Response
irPD	immune-related Progressive Disease
irPR	immune-related Partial Response
irSD	immune-related Stable Disease
irBOR	immune-related Best Overall Response

13.5.3 Baseline Assessment Using Immune-Related Response Criteria (irRC)

- Step 1: Identify the index lesions (five lesions per organ, up to ten visceral lesions and five cutaneous lesions).
- Step 2: Calculate the Sum of the Products of the two largest perpendicular Diameters (SPD) of all of these index lesions:

$$SPD = \sum_i (\text{Largest diameter of lesion } i) \times (\text{Second largest diameter of lesion } i)$$

13.5.4 Post-baseline Assessments Using irRC

- Step 1: Calculate the SPD of the index lesions.
- Step 2: Identify new, measurable lesions ($\geq 5 \times 5$ mm; up to five new lesions per organ: five new cutaneous lesions and ten visceral lesions).

- Step 3: Calculate the SPD of the new, measurable lesions.
- Step 4: Calculate the tumor burden:

$$\text{Tumor burden} = \text{SPD}_{\text{index lesions}} + \text{SPD}_{\text{new, measurable lesions}}$$

- Step 5: Calculate the change in tumor burden relative to baseline and the change in tumor burden relative to nadir.
- Step 6: Derive the overall response using the table below:

Overall Response	Criterion
irCR	Complete disappearance of all lesions (whether measurable or not, and no new lesions) confirmed by a repeat, consecutive assessment ≥ 4 weeks from the date first documented.
irPR	Decrease in tumor burden $\geq 50\%$ relative to baseline confirmed by a consecutive assessment ≥ 4 weeks from the date first documented.
irSD	Criteria for irCR, irPR, and irPD are not met; does not require confirmation.
irPD	Increase in tumor burden $\geq 25\%$ relative to nadir confirmed by a consecutive assessment ≥ 4 weeks from the date first documented.

irCR = immune-related complete response; irPD = immune-related progressive disease; irPR = immune-related partial response; irSD = immune-related stable disease.

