8.3. Extent of Disease Assessment

Tumor response will be evaluated according to the Response Evaluation Criteria in Solid Tumors (RECIST) version 1.1, to establish disease progression by CT or MRI. In addition, other radiographic or scintigraphic procedures (such as radionuclide bone scans), as deemed appropriate by the investigator, will be performed to assess sites of neoplastic involvement. The same method of assessment should be used throughout the study. Investigators should select target and non-target lesions in accordance with RECIST v1.1 guidelines. Follow-up measurements and overall response should also be in accordance with these guidelines. To be assigned a status of confirmed PR or CR, changes in tumor measurements should be confirmed by repeated assessments that should be performed \geq 30 days after the criteria for response are first met.

The extent of disease assessment should be completed until it has been determined the patient has progressive disease (in accordance with RECIST v1.1). In the event the patient discontinues study treatment for reasons other than disease progression, an extent of disease assessment should be completed as soon as possible relative to the date of study termination to ensure disease progression is not present and to assess overall disease status. In such patients, this assessment should occur no later than 28 days after a patient's last treatment with avelumab (and prior to any subsequent anti-cancer therapy).

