9.4. Discontinuation of Study Treatment

Discontinuation of study treatment will be required if deemed by the investigator to be in the subject's best interest or if subject meets any of the criteria for study withdrawal listed below:

- Disease progression as assessed by RECIST 1.1 criteria (Appendix 1), unless the subject meets criteria for treatment beyond progression (Section 9.7);
- Termination of the study by Vanderbilt or relevant regulatory authority;
- Drug availability or study supply discontinued;
- The patient withdraws consent to undergo further treatment;
- The patient is lost to follow-up, refuses further follow-up, or is noncompliant;
- The patient no longer requires treatment (e.g. patients having experienced a tumor reduction followed by resection and no longer with evaluable disease);
- Initiation of treatment with another anti-cancer therapy;
- Additional protocol specified reason for discontinuation (e.g. related to adverse event), see Section 11.

In the case of pregnancy, the investigator must immediately notify the EMD Serono medical designee of this event. In most cases, the study drug will be permanently discontinued in an appropriate manner. If the investigator determines a possible favorable benefit/risk ratio warrants continuation of study drug, a discussion between the investigator and appropriate internal and external entities must occur (e.g. the IRB and the EMD Serono medical designee).

If a patient does not return for a scheduled visit, every reasonable effort should be made to contact the patient. In any circumstance, every reasonable effort should be made to document subject outcome, if possible. The investigator should inquire about the reason for withdrawal, request the patient to return for a final visit, if applicable, and follow-up with the patient regarding any unresolved treatment-related adverse events.

All subjects who discontinue study drug should comply with protocol specified follow-up procedures as outlined in Section 7. The only exception to this requirement is when a subject withdraws consent for all study procedures including post-treatment study follow-up or loses the ability to consent freely (e.g. is imprisoned or involuntarily incarcerated for the treatment of either a psychiatric or physical illness).

If study drug is discontinued, the reason for the discontinuation must be documented in the subject's medical records and entered on the appropriate CRF page.

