9.7. Treatment After Initial Evidence of Radiologic Disease Progression

Immunotherapeutic agents such as avelumab may produce antitumor effects by potentiation of endogenous cancer-specific immune responses. The response patterns seen with such an approach may extend beyond the typical time course of responses seen with cytotoxic agents, and can manifest as a clinical response after an initial increase in tumor burden or even the appearance of new lesions.

Subjects treated with avelumab will be permitted to continue treatment beyond initial RECIST 1.1 defined progressive disease (PD) while waiting for confirmation of PD if they are clinically stable as defined by the following criteria:

- Investigator-assessed clinical benefit and absence of rapid disease progression
- Tolerating study drug

- Stable performance status
- Absence of progressive tumor at critical anatomical sites (e.g. cord compression) requiring urgent alternative medical intervention.

The assessment of clinical benefit should be balanced by clinical judgment as to whether the subject is clinically deteriorating and unlikely to receive any benefit from continued treatment with avelumab.

All decisions to continue treatment beyond initial progression should be documented in the study records. The subject will continue to receive monitoring according to the Schedule of Assessments listed in Section 7.

If radiologic imaging shows initial disease progression, repeat scanning and tumor assessment should be performed 4 to 6 weeks later in order to confirm the observation, unless an alternative rescanning interval is provoked by clinical deterioration.

Assigned study treatment may be continued at the investigator's discretion while awaiting radiologic confirmation of disease progression. In determining whether or not the tumor burden has increased or decreased, investigators should consider all target as well as non-target lesions. **For subjects continuing avelumab beyond initial progression, further disease progression is defined as an additional 10% increase in tumor burden volume from time of initial PD.** This includes an increase in the sum of all target lesions and/or the development of new measurable lesions. For subjects with evaluable disease only, further progression is defined as unequivocal disease progression of non-target lesions or the development of new measurable lesions from time of initial PD.

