13.5.5 Determination of Immune-Related Best Overall Response (irBOR)

Once a patient has completed all tumor assessments, his/her irBOR may be determined:

Condition	irBOR
At least one irCR	irCR
At least one irPR and no irCR	irPR
At least one irSD and no irCR and no irPR	irSD
At least one irPD and no irCR, no irPR, and no irSD	irPD

irBOR = immune-related best overall response; irCR = immune-related complete response; irPD = immune-related progressive disease; irPR = immune-related partial response; irSD = immune-related stable disease.

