- Overall immune-related stable disease (irSD):

Sum of the diameters (longest for nonnodal lesions, shortest for nodal lesions) of target and new measurable lesions is neither irCR, irPR, (compared to baseline) or immune-related progressive disease (irPD, compared to nadir).

- **Overall immune-related progressive disease (irPD):**
Sum of the diameters (longest for non-nodal lesions, shortest for nodal lesions) of target and new measurable lesions increases $\geq 20\%$ (compared to nadir), confirmed by a repeat, consecutive observation at least 4 weeks from the date first documented.

New measurable lesions: Incorporated into tumor burden (i.e. added to the target lesion measurements). A lymph node has to be ≥ 15 mm in short axis to be a measurable new lesion and its short axis measurement is included in the sum. Up to 2 new lesions per organ and up to 5 new lesions in total can be added to the measurements.

New non-measurable lesions: Do not define progression but preclude irCR.

Overall responses derived from changes in index, non-index, and new lesions are outlined in the below table:

Overall Response Derived from Changes in Index, Non-index and New Lesions:

Measurable response	Non-measurable response		Overall response using irRECIST ^b
	Non-Index Lesions	Measurable Lesions	
Index and New Measurable Lesions (Tumor Burden)^a			
Decrease 100%	Absent	Absent	irCR
Decrease 100%	Stable	Any	irPR
Decrease 100%	Unequivocal progression	Any	irPR
Decrease $\geq 30\%$	Absent/stable	Any	irPR
Decrease $\geq 30\%$	Unequivocal progression	Any	irPR
Decrease $< 30\%$ and increase $< 20\%$	Absent/stable	Any	irSD
Decrease $< 30\%$ and increase $< 20\%$	Unequivocal progression	Any	irSD
Increase $\geq 20\%$	Any	Any	irPD

a. Decrease assessed relative to baseline.

b. Response (irCR and irPR) and progression (irPD) must be confirmed by a second, consecutive assessment at least 4 weeks apart.

Appendix 3

Cockcroft-Gault (CG) equation for the estimation of creatinine clearance

$$eCrCl \text{ (mL/min)} = \frac{(140 - \text{age in years}) \times (\text{weight in kg}) \times (0.85 \text{ if female})}{72 \times (\text{serum creatinine in mg/dL})}$$

Appendix 4

Acceptable Contraception

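### Under irRC, growth past the progression threshold that no later scan confirms is scored as stable disease

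*Combined protocol and SAP*

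**What the plan says.** **Time-point response (13.5.4).** irPD is a rise in tumor burden of at least 25% "relative to nadir confirmed by a consecutive assessment ≥ 4 weeks from the date first documented". irSD is the remainder: "Criteria for irCR, irPR, and irPD are not met; does not require confirmation".

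**Best response (13.5.5).** irSD is assigned on "At least one irSD and no irCR and no irPR". irPD is assigned only on "At least one irPD and no irCR, no irPR, and no irSD". The table has four outcomes. The RECIST table in 13.3.5, by contrast, has a not-evaluable entry.

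**When scans stop.**
- Section 9.4 ends treatment on "Disease progression as assessed by RECIST 1.1 criteria (Appendix 1), unless the subject meets criteria for treatment beyond progression (Section 9.7").
- Section 9.7 asks for a repeat scan 4 to 6 weeks after initial progression, "unless an alternative rescanning interval is provoked by clinical deterioration". It does not say how to score the patient if that scan is not done.
- Note 19 to 7.1, and 7.6, continue post-treatment imaging only for patients who left for a reason other than progression shown on CT or MRI.
- Section 8.3 is to the same effect: "The extent of disease assessment should be completed until it has been determined the patient has progressive disease".

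**Appendix 2 (irRECIST).** The footnote to the table says that "progression (irPD) must be confirmed by a second, consecutive assessment at least 4 weeks apart". The text defines irSD as a remainder, but the table limits it to an increase below 20%.

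**Reporting (17.4).** Categories 4 to 9, which include progressive disease, early deaths and unknown, count as treatment failure. Stable disease does not. A main analysis of a clinical benefit rate is planned, but the rate is not defined and the criteria set is not named.

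**The concern.** A remainder category with no bound on growth works only if every patient who crosses the progression threshold gets a confirming scan. Patients who die, deteriorate, start another therapy or stop imaging first will not get one, and these tend to be the patients who are doing worst. As written, the irRC tables call them stable.

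The results at stake are descriptive: the distribution of immune-related best response and, if they rest on irRC, the clinical benefit rate in 17.4 and the correlations of PD-L1, MSI status and lymphocyte infiltration with clinical benefit announced in 2.2. Section 13.1 assesses response and progression by both RECIST 1.1 and irRC, and 17.1 names both for best response, so irRC results will be reported.

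**Working it through.** **1. The plan's own figures.** From 17.3: n = 25, null rate 5%, alternative 21%, success if X ≥ 4, where X is the number of responders.

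- Attained alpha: P(X ≥ 4 | n = 25, p = 0.05) = 0.0341, within the one-sided 5%.
- Power: P(X ≥ 4 | n = 25, p = 0.21) = 0.8013, against the stated 80%.

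Both reproduce. irSD and irPD each add 0 to X, so moving a patient between them changes neither figure.

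**2. The irRC tables applied as written.** Take a patient with no confirmed irCR or irPR whose first re-scan shows the growth below.

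| Growth over nadir | No later scan | Confirmed at least 4 weeks later |
|---|---|---|
| 30% | irSD | irPD |
| 100% | irSD | irPD |
| 300% | irSD | irPD |

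In the middle column irCR, irPR and irPD all fail, so irSD follows at that scan, and 13.5.5 makes it the best response.

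The right-hand column assumes that confirmed irPD is dated back to the first scan, which the plan does not state. If the first scan is scored irSD while confirmation is awaited, even a confirmed progressor has one irSD, and 13.5.5 again returns irSD.

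**3. The same patient under RECIST 1.1.** Section 13.3.2 calls progression at a 20% rise in the sum of diameters with at least 5 mm absolute growth, or at a new lesion, and needs no confirmation. irRC uses products of two diameters. If all lesions grow evenly:

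- +100% in the product is √2 = 1.414, or +41% in diameter. This is RECIST progression if the 5 mm condition is met.
- +25% in the product is √1.25 = 1.118, or +12% in diameter. This is below the RECIST threshold.

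The two criteria sets can therefore disagree sharply on large growth, but RECIST will not call every affected patient progressive.

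**4. How many patients.** The documents give no rate. Assume that 40-60% of 25 progress at the first re-scan and 30-60% of those have no valid confirming scan.

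- Low: 25 × 0.4 × 0.3 = 3 patients, 3/25 = 12 percentage points.
- High: 25 × 0.6 × 0.6 = 9 patients, 9/25 = 36 percentage points.

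**5. Effect on a clinical benefit rate built on irRC.** Assume that the rate is responders plus stable disease, with 4 responders, 6 truly stable patients and 15 whose first re-scan already meets the threshold.

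| Progressors lacking confirmation | Counted as benefit | Rate | Wilson 95% interval |
|---|---|---|---|
| 0 | 4 + 6 + 0 = 10 | 40% | 23.4-59.3 |
| 4 | 4 + 6 + 4 = 14 | 56% | 37.1-73.3 |
| 8 | 4 + 6 + 8 = 18 | 72% | 52.4-85.7 |
| 15 | 4 + 6 + 15 = 25 | 100% | 86.7-100 |

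With 3 truly stable patients (18 progressors), 9 unconfirmed move the rate from 7/25 = 28% to 16/25 = 64%. With 10 truly stable (11 progressors), 6 unconfirmed move it from 14/25 = 56% to 20/25 = 80%. The response rate stays at 4/25 = 16% throughout.

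**The case against.** The best reply is that the plan asks for the confirming scan, runs RECIST 1.1 alongside, and names no disease-control rate among its objectives. Much of this stands, and it rules out several stronger readings.

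- **That confirmation is missing by design.** A reader might infer that only clinically stable patients are re-scanned. In 9.7 the stability criteria govern continued treatment; the request for a scan at 4 to 6 weeks is not limited to those patients. The exception speaks of an alternative interval, not an earlier one, although a scan before 4 weeks could not confirm irPD. An end-of-treatment scan is due unless one was done in the previous 28 days, so when it is done it can serve as confirmation. A recent progression scan, however, removes the need for it.
- **That 17.4 fails to catch these patients.** It counts progressive disease and unknown as failures, as well as early deaths. But it does not say whether RECIST or irRC feeds its categories, and 13.5.4 gives these patients a definite irSD, not unknown.
- **That Appendix 2 has the same defect.** Only its text does. Under its table an unconfirmed rise of 20% or more cannot be irSD, and the footnote bars irPD, so it has no clear category.
- **That duration of response is inflated.** Section 13.4.1 ends a response at the first objectively documented progression and needs no confirmation; no separate irRC duration is defined.
- **That the biomarker objective is biased.** Section 3.2 concerns association with response, and responder status does not move. Only the clinical-benefit wording in 2.2 is exposed.
- **That the result would be judged against 52%.** That disease control rate in 4.1 is background on second-line chemotherapy, not a benchmark set for this trial.

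The reply does not supply a scoring rule for a patient whose confirming scan is not done.

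**Conclusion.** The concern holds as a defect in a stated scoring rule. Under 13.5.4 and 13.5.5, growth of 25% or more over nadir with no later evaluable scan becomes irSD, and irSD becomes the best response unless the patient has a confirmed irCR or irPR. RECIST 1.1 may record the same patient as progressive.

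The primary result is safe: response rate, decision rule, alpha and power are unchanged. The distribution of immune-related best response is biased in the drug's favour. The clinical benefit rate in 17.4 and the correlations in 2.2 share that bias only if they use irRC.

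The size is not known from the documents. The 3 to 9 patients of 25, and the example that rises from 40% to 72%, rest wholly on the stated assumptions. A patient with an earlier scan below the threshold is properly irSD and is not part of the count. The rule should be settled before analysis.

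**What to change.** 1. In 13.5.4, 13.5.5 and Appendix 2, state that an increase meeting the irPD threshold with no later evaluable scan at least 4 weeks afterwards is irPD, dated at the first scan. It is overturned only by a later scan that shows no progression. An equivalent option is a separate unconfirmed-progression category that counts as failure in 17.4.
2. State that irSD requires a scan below the irPD threshold, and that confirmed irPD is dated to the first scan.
3. Align the Appendix 2 text with its table.
4. In 17.4, define the clinical benefit rate and say which criteria set feeds the response categories.

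The cost is a few sentences. No scans are added and no treatment rule changes, and the allowance for delayed response after initial growth is kept. Stable-disease and clinical-benefit figures become somewhat less favourable.

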13.5.5 Determination of Immune-Related Best Overall Response (irBOR)

Once a patient has completed all tumor assessments, his/her irBOR may be determined:

Condition	irBOR
At least one irCR	irCR
At least one irPR and no irCR	irPR
At least one irSD and no irCR and no irPR	irSD
At least one irPD and no irCR, no irPR, and no irSD	irPD

irBOR = immune-related best overall response; irCR = immune-related complete response; irPD = immune-related progressive disease; irPR = immune-related partial response; irSD = immune-related stable disease.

13.6. Response Review and Central Tumor Assessments

All responses, if any, may be reviewed by an expert(s) independent of the study at the study's completion. In addition, at the end of treatment, all scans (baseline and through disease progression) may be requested via a CD and sent to the Vanderbilt Cancer Imaging Support Laboratory for central review and assessment.

14. SAFETY REPORTING of ADVERSE EVENTS

14.1. General

Safety assessments will consist of monitoring and reporting AEs and SAEs that are considered possibly, probably or definitely related to avelumab, all events of death, and any study-specific issue of concern.

Adverse event collection and reporting is a routine part of every clinical trial. Each adverse event will be graded according to the NCI's Common Terminology Criteria for Adverse Events (NCI CTCAE), Version 4.03, dated June 14, 2010, currently locatable via the following URL:

< http://evs.nci.nih.gov/ftp1/CTCAE/CTCAE_4.03_2010-06-14_QuickReference_8.5x11.pdf >.

For events not listed in the CTCAE, severity will be designated as mild, moderate, severe or life threatening, or fatal which respectively correspond to Grades 1, 2, 3, 4, and 5 on the NCI CTCAE, with the following definitions:

- **Mild:** An event not resulting in disability or incapacity and which resolves without intervention;
- **Moderate:** An event not resulting in disability or incapacity but which requires intervention;
- **Severe:** An event resulting in temporary disability or incapacity and which requires intervention;
- **Life-threatening:** An event in which the patient was at risk of death at the time of the event;
- **Fatal:** An event that results in the death of the patient.

Information on all adverse events, whether serious or not, whether reported by the participant, directly observed, or detected by physical examination, laboratory test or other means, will be collected, recorded, followed and reported as described in the following sections.

Reporting period: Adverse events experienced by participants will be collected and reported from initiation of study medication, throughout the study, and within 30 days of the last dose of study medication. Participants who experience an ongoing adverse event related to a study procedure and/or study medication beyond 30 days will continue to be contacted by a member of the study team until the event is resolved, stabilized, or determined to be irreversible by the participating investigator.

Laboratory and vital sign abnormalities are to be recorded as Adverse Events only if they are medically relevant as judged by the investigator (e.g. symptomatic, requiring corrective treatment, leading to discontinuation and/or fulfilling a seriousness criterion). Unless otherwise specified by protocol or a patient's study physician, abnormal laboratory values of Grade 1 and Grade 2 will be deemed Not Clinically Significant (NCS) and are not required to be individually noted or recorded within the study data.

Baseline disease-related signs and symptoms which are initially recorded as medical history, will subsequently be recorded as adverse events during the trial if they worsen in severity or increase in frequency.

Participants should be instructed to report any serious post-study event(s) that might reasonably be related to participation in this study. The investigator should notify the IRB and any other

applicable regulatory agency of any unanticipated death or adverse event occurring after a participant has discontinued or terminated study participation that may reasonably be related to the study.

